11. MANAGEMENT AND REPORTING OF ADVERSE EVENTS/SERIOUS ADVERSE EVENTS

argenx or its designee will follow all applicable local and national regulatory requirements related to safety reporting. Study investigators must also comply with the applicable regulatory requirements for reporting of serious events to the IRB/IEC/Ethics Committees/Regulatory authorities (if applicable) responsible for reviewing information from the study at their site. All serious and non-serious AEs, pregnancies, and special situations will be collected. Once the treating physician becomes aware of AEs and SAEs should be reported to the sponsor on an AE/SAE Report Form as soon as possible, but no later than within 24 hours for Serious AEs and 7 calendar days for non-serious AEs, pregnancies and special situations of the site becoming aware of the event, along with an assessment of severity and causality. argenx will receive, process and submit these reports to the relevant health authorities as appropriate.

All AEs will be collected from signing the informed consent until the end of study participation, loss to follow up, consent withdrawal or death. After the initial AE/SAE report, the treating physician should make every effort to follow each participant until resolution, stabilization, the event is otherwise explained, or the participant is lost to follow-up. The action taken for AEs occurring in the efgartigimod cohort should be provided by the treating physician.

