With the exception of AChE inhibitors, the complement inhibitor eculizumab, and a liquid formulation of azathioprine, which have received regulatory approval in Europe for the treatment of gMG, all other existing therapies are used off-label [Vyvgart EPAR].

In the United States (US), efgartigimod is approved for the indication of gMG in adult patients who are AChR antibody positive and in the EU it is approved as an add-on to standard therapy for the treatment of adult patients who are AChR antibody positive.

The recommended dose of efgartigimod is 10 mg/kg as a 1-hour intravenous infusion to be administered in cycles of once weekly infusions for 4 weeks. Subsequent treatment cycles are administered according to clinical evaluation. The frequency of treatment cycles may vary by patient.

In the EU Risk Management Plan (RMP) for efgartigimod, serious infections, is considered to be an important potential risk. As efgartigimod induces a transient lowering in IgG levels, there is a potential

risk for infections associated with the lowered IgG levels. In the randomized placebo-controlled study of 167 patients ARGX-113-1704, 84 patients with gMG were exposed to efgartigimod and the most frequently observed adverse reactions were upper respiratory infections (10.7% in the efgartigimod patients and 4.8% in the placebo patients) and urinary tract infections (9.5% in the efgartigimod patients and 4.8% in the placebo patients). In the patients who received efgartigimod, these events were \leq Grade 2 according to the Common Terminology Criteria for Adverse Events (CTCAE). Overall, treatment emergent infections were reported in 46.4% of patients treated with efgartigimod and 37.3% of patients treated with placebo. The frequency of infections in the efgartigimod treated patients did not increase with repeated cycles of treatment. There were no serious infections or opportunistic infections in the efgartigimod treated patients. This study will evaluate the occurrence of serious infections in gMG patients treated with efgartigimod in the real world setting under conditions of normal clinical practice compared to gMG patients who are not treated with efgartigimod.

During clinical development of the IV formulation, in the efgartigimod phase 3 placebo-controlled 26 week clinical study, ADAPT, there were 2 reported neoplasm events, 1 (1.2%) in the efgartigimod treatment arm and 1 (1.2%) in the placebo treatment arm.

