9.2.1 Selection of Study Population

Patients with gMG who are expected to start treatment with efgartigimod at enrolment or are within their first cycle of efgartigimod at enrolment will be eligible to enrol into the efgartigimod cohort. Patients with gMG who have not been exposed to efgartigimod and for whom it is not planned to start

treatment with efgartigimod at enrolment will be eligible to enrol into the non-efgartigimod cohort.

Physicians participating in the study will be instructed to invite all patients who meet study eligibility criteria to enrol until the enrolment period is closed.

Inclusion Criteria (efgartigimod cohort)

1. Patients diagnosed with gMG who are expected to start commercial efgartigimod at enrolment or who are within their first cycle of efgartigimod at enrolment
2. Have provided appropriate written informed consent

Inclusion Criteria (non-efgartigimod cohort)

3. Patients diagnosed with gMG who have not been exposed to efgartigimod and for whom it is not planned to start treatment with efgartigimod at enrolment
4. Have provided appropriate written informed consent

Exclusion Criteria

None

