gMG treatments at or following enrollment (excluding efgartigimod)	
 Drug name, dose, start and stop dates 
 Acetylcholinesterase inhibitors Corticosteroids Other Immunosuppressants (specify) Monoclonal antibodies (specify) Plasmapheresis/plasma exchange acute Plasmapheresis/plasma exchange chronic IVIg therapy acute IVIg therapy chronic Other 	✓	✓

Category	Variables	Baseline	Follow up
Efgartigimod treatment	
 • Date of administration • Reason for interruption during cycle of treatment • Reason for permanent discontinuation whilst on study 	✓	✓
Other comedications at or following enrollment for conditions other than gMG	
 • Drug name, start and stop dates • Indication 	✓	✓
Live/attenuated vaccinations 2 months prior to enrollment to 2 months after last Vyvgart dose	
 • Live/attenuated vaccine 
 ○ Vaccine ○ Date 	✓	✓
Adverse Events (AEs)/Serious Adverse Events (SAEs)	
 • AEs, SAEs 		✓
Events of interest	See Table 2		✓

*All variables will be collected ONLY if available as part of routine clinical practice

A patient will be considered to be an efgartigimod exposed patient if he/she has received at least one dose of efgartigimod.

Additionally, taking into account the variable follow up time and time interval between cycles, the following will be measured for efgartigimod:

- Number of administrations per year
- Total duration of the exposure
- Total number of administrations

The exposure time window of efgartigimod is 56 days +/-3 days after the last dose.

Events of interest in this study will be pre-specified as per [Table 2](#) below.

Table 2: Pre-specified events of interest

Event of interest	Definition	Measurement
Serious infection	Any serious adverse event coded to the Medical Dictionary for Regulatory Activities (MedDRA) System Organ Class (SOC) of Infection and Infestation. See Section 11 for definition of Serious.	Proportion of patients who report serious infections during the course of the study in the efgartigimod treated cohort compared to the non-efgartigimod cohort. Incidence rate of serious infections per patient-years exposed in the efgartigimod treated cohort compared to the non-efgartigimod cohort.

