9.7 Data Analysis

The Full Population will be all patients enrolled.

The Safety Population will include all patients enrolled who have taken at least one dose of efgartigimod for the efgartigimod cohort and all patients enrolled into the non-efgartigimod cohort. All analysis will be based on the Safety Population.

Unless otherwise specified, categorical endpoints will be summarised using counts and percent; continuous endpoints will be summarised using mean, standard deviation, median, minimum and maximum values. Statistical analysis will be mainly descriptive in nature using metrics such as

incidence proportion, exposure-adjusted incidence rate, confidence intervals, etc. Details of the analysis plan will be specified in the Statistical Analysis Plan (SAP).

Primary objective

Descriptive statistics will be used to summarise the long-term safety of efgartigimod, including the occurrence of events of serious infections, in gMG patients treated with efgartigimod compared to gMG patients not exposed to efgartigimod. The number and percentage of patients with AEs/SAEs will be presented. The rate per person-year exposure with a 95% CI will be constructed using asymptomatic normal approximation.

Although no formal hypothesis will be tested in the study, statistical models will be used to test the difference of incidence between treatment cohorts (efgartigimod vs. comparator). Two base models which are widely used to model incidence proportion and incidence rate adjusted by potential confounders will be used:

1. To model incidence proportions, a logistic regression model will be used including patients with event vs. patients without event as the response variable and treatment group and country as covariates.
2. To account for varied follow-up time, a Cox regression model will be used with time to the first occurrence of event for each patient as the response variable, treatment group and country as covariates .

Countries with small sample sizes will be combined with other countries based on the geographic locations. Other covariates may be added to the above base models as described below.

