10. PROTECTION OF HUMAN PATIENTS

Prior to any data collection under this protocol, a written ICF must be signed by the patient/legal guardian in accordance with local practice and regulations. Information about the study will be explained to the patient/legal guardian where appropriate including advice that the patient can withdraw from the study at any time. A copy of the ICF, signed and dated by the patient/legal guardian, must be given to the patient/legal guardian. Confirmation of a patient/legal guardian's informed consent must be documented in the patient's medical records prior to any data collection under this protocol. The ICF must not be altered without the prior agreement of the relevant IRB/IEC and argenx.

The participant must be informed that his/her personal study-related data will be used by the Sponsor in accordance with local data protection law. The level of disclosure must also be explained to the participant who will be required to give consent for their data to be used as described in the informed consent.

The participant must be informed that his/her medical records may be examined by auditors or other authorized personnel appointed by the Sponsor, by appropriate IRB/IEC members, and by inspectors from regulatory authorities.

Participants will be assigned a unique identifier. Any participant records or datasets that are transferred to the Sponsor will contain the identifier only; participant names or any information which would make the participant identifiable will not be transferred.

Documents that are not for submission to the study (e.g., ICF), will be maintained by the site in strict confidence, except to the extent necessary to allow monitoring by argenx or its representative, and auditing by argenx and regulatory authorities. No documents identifying patients by name will leave the clinical site and patient identity will remain confidential in all publications related to the study.

Prior to the collection of any study related data, IRB/IEC approval of the protocol, informed consent, and all patient enrolment materials will be obtained in each country and for each site, as applicable. The study will be conducted in accordance with the ethical principles originating from the Declaration of Helsinki, applicable privacy laws, and local regulations for each participating site.

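### Patients enrolled during their first efgartigimod cycle have doses on record before consent, but no adverse events from those days

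*Protocol*

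**What the plan says.** Entry to the efgartigimod cohort (section 9.2.1) is open to patients "expected to start commercial efgartigimod at enrolment or who are within their first cycle of efgartigimod at enrolment". Section 7 describes treatment as "administered in cycles of once weekly infusions for 4 weeks", so someone already in the first cycle may have had several infusions by the time of consent.

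Event collection has a different starting point. Section 11: "All AEs will be collected from signing the informed consent until the end of study participation". Section 10 sets the same boundary for all data: "Prior to any data collection under this protocol, a written ICF must be signed by the patient/legal guardian".

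Table 1 in section 9.3 ticks efgartigimod administration dates at both baseline and follow-up. It ticks AEs/SAEs and events of interest at follow-up only. Previous infections are recorded at baseline, as medical history.

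Exposure is a patient-level attribute: "A patient will be considered to be an efgartigimod exposed patient if he/she has received at least one dose of efgartigimod". The exposure window in section 9.3 has an end (56 days, plus or minus 3, after the last dose) but no stated start. The Cox model in section 9.7 has no stated time origin.

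**The concern.** For a mid-cycle enrolee, the database will show infusions given before consent and nothing about what happened after them. An infection in that interval can appear only as baseline history, which is not an outcome. This is a matter of what the eCRF collects, so the SAP cannot repair it.

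Section 7 names the lowering of IgG as the mechanism of the potential infection risk, and the first cycle is the first time it occurs. The loss may also be selective, because a patient who becomes seriously ill or dies after an early infusion is less likely to be enrolled. That is left truncation at consent.

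Two planned analyses are exposed:

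- **Rates per exposed patient-year (Table 2).** If exposure is counted from the recorded first dose, the pre-consent days enter the denominator although no event in them could be counted.
- **Time since last administration in 4-week intervals (section 9.7).** With weekly infusions, every lost day lies within a week of a dose, so the whole loss falls in the first interval.

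**Working it through.** **The plan's own figures.** Clopper-Pearson limits at n = 270 and 20% are 15.4% to 25.3%, which matches the planned 5-point half-width. Inflation for 20% dropout gives 270 / 0.80 = 337.5, or 338 against the stated 340. The sample size is not in dispute.

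**Length of the gap.** Four weekly infusions fall on days 0, 7, 14 and 21 (section 7). Adding the 56-day window (section 9.3) gives a first-cycle window of 21 + 56 = 77 days. Consent at the second, third or fourth infusion leaves:

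- 7/77 = 9%
- 14/77 = 18%
- 21/77 = 27%

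In the first 4-week interval since last administration, an uninterrupted first cycle contributes 21 + 28 = 49 days, of which up to 21 (43%) are unobserved. Later cycles dilute this.

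**Serious infections missed, upper bound.** Assume all 340 patients consent on day 21 and the hazard is constant: h = -ln(1 - p)/T, and probability over 21 days = 1 - exp(-h × 21/365.25). The source rates are in section 9.5. The 5-year and 10-year periods for the assumed 20% are the limits of follow-up.

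| Rate | h per year | 21-day probability | Patients of 340 |
|---|---|---|---|
| 20% over 10 years | 0.0223 | 0.128% | 0.44 |
| 20% over 5 years | 0.0446 | 0.256% | 0.87 |
| 6.2% over 1.7 years (ADAPT+) | 0.0377 | 0.216% | 0.74 |
| 33.4% over 5.4 years (population cohort) | 0.0753 | 0.432% | 1.47 |

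The bound is about 0.4 to 1.5 patients, or 0.1 to 0.4 percentage points. If a cycle is read as four full weeks and consent comes at day 28, the range is 0.6 to 2.0 patients. If the first-cycle hazard were five times the ADAPT+ average (assumption), 21 days would carry 1.08%, or 3.7 patients.

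**All infections, same worst case.** Section 7 gives 46.4% on efgartigimod and 37.3% on placebo. I assume these refer to the 26-week period that section 7 gives for ADAPT; the protocol does not say that the two descriptions are of one study.

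- Efgartigimod: -ln(1 - 0.464)/182 = 0.00343 per day. Over 21 days that is 6.9%, or about 24 of 340.
- Placebo by the same method: 5.2%, or about 18 of 340. The excess is about 6 patients.
- If half the cohort (170) enrolled mid-cycle at day 10 on average (assumption): 170 × 10 × 0.00343 = about 6 patients with any infection.

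The protocol does not give the share enrolled mid-cycle, so these are bounds and scenarios, not estimates.

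**The case against.** The strongest reply is that the study is about long-term safety. At most three weeks are lost from 5 to 10 years of follow-up, at least 56 of the 77 first-cycle days remain observed, and the effect on serious infection is well inside the planned 5-point half-width. That stands, and it limits the importance of the point.

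It can also be said that nothing is wholly invisible. Infection history is taken at baseline, a legal guardian may consent for a patient, and section 9.2 requires a log of eligible patients who do not enrol, with reasons. These soften the selection argument. They do not turn an early event into a recorded outcome.

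A reader might draw three stronger conclusions, which the document does not support:

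- **That events between consent and first dose will be counted against efgartigimod.** The patient-level exposure rule and the Safety Population ("The Safety Population will include all patients enrolled who have taken at least one dose of efgartigimod for the efgartigimod cohort") allow that reading, most clearly for the proportion. But these events are collected, and consent and administration dates are recorded. The Table 2 rate can be read as excluding pre-dose time, and the Annex 2 checklist leaves exposure details to the SAP. This is an analysis rule that may already be settled there.
- **That lost early events and miscounted pre-dose events cannot be disentangled.** They arise in different patients, who are identified by comparing the consent date with the first administration date.
- **That the comparator cohort has no such gap.** Comparators need only be unexposed to efgartigimod. They may have taken other immunosuppressants for years, so the early risk period of those drugs also precedes consent.

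**Conclusion.** The point holds in a limited form. Mid-cycle enrolees contribute recorded doses without recorded outcomes for up to about 21 days, at most 27% of the first-cycle window, and entry may be selective against those with early events.

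For the 5-to-10-year serious-infection proportion the effect is small: at most about 0.4 to 1.5 of 340 patients, assuming a constant hazard at the protocol's rates and consent by every patient at the fourth infusion. The figure of about 24 patients should not be read as missed serious infections or as excess risk. It covers infections of any severity in that same worst case, and placebo by the same method gives about 18.

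What remains is under-ascertainment, by an unknown amount, of early AEs and of the first interval in the time-since-last-administration analysis. It is worth correcting because it must be settled at data collection and is cheap.

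**What to change.** 1. **Section 11 and Table 1:** for patients enrolled mid-cycle, abstract AEs and SAEs from first dose to consent out of the medical record once consent is signed. Flag them as pre-enrolment and report them separately. Section 10 bars data collection before consent, not chart review afterwards, and Table 1 already takes pre-enrolment treatments and infection history.
2. **Section 9.7:** start counted events and person-time in the efgartigimod cohort at the later of first dose and consent, so that numerator and denominator cover the same days. List consent-to-first-dose events separately. The flagged pre-enrolment events then stay outside the rates and the Cox model, where they would have no matching time at risk.
3. **Sensitivity analysis:** repeat the main comparisons with the efgartigimod cohort restricted to patients enrolled on or before first dose.

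The cost is wording in the protocol and eCRF, about three weeks of chart per mid-cycle patient at most, and one further analysis. The abstracted events come only from patients who went on to consent, so they narrow the gap without removing the selection. That is a further reason to report them apart.

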11.1 Definitions

AE: Any untoward medical occurrence in a patient administered a pharmaceutical product or device and that does not necessarily have a causal relationship between the product and the event. An AE can, therefore, be any unfavorable or unintended sign (including an abnormal laboratory finding) or symptom temporally associated with a medicinal product, whether or not related to the medicinal product.

SAE: Any untoward medical occurrence which:

- Results in death.
- Is life-threatening: The term life threatening in the definition of serious refers to an event in which the participant was at risk of death at the time of the event. It does not refer to an event, which hypothetically might have caused death, if it were more severe.
- Requires inpatient hospitalization or prolongs hospitalization: In general, hospitalization signifies that the participant has been admitted at the hospital or emergency ward for observation and/or treatment that would not have been appropriate in the physician's office or outpatient setting. Complications that occur during hospitalization are AEs. If a complication prolongs hospitalization or fulfills any other seriousness criteria, the event will be considered serious. When in doubt as to whether hospitalization occurred or was necessary, the AE is considered serious. Hospitalization for elective treatment of a pre-existing condition that did not worsen from screening will not be collected as an AE.
- Results in persistent or permanent disability or incapacitation: The term disability means a substantial disruption of a person's ability to conduct normal life functions. This definition is not intended to include events of relatively minor medical significance such as uncomplicated headache, nausea, vomiting, diarrhea, influenza, and accidental trauma (e.g., sprained ankle) that can interfere with or prevent everyday life functions but do not constitute a substantial disruption.

- Results in a congenital anomaly or birth defect.
- Other situations: Any important medical event that may not be immediately life-threatening or result in death or hospitalization but, based upon appropriate medical judgment, may jeopardize the patient or may require medical or surgical intervention to prevent one of the other outcomes listed in the definition above, should also be reported as an SAE.

Special situations:

- Off-label use: situations where a medicinal product is intentionally used for a medical purpose not in accordance with the authorized product information.
- Overdose: administration of a quantity of a medicinal product given per administration or cumulatively which is above the maximum recommended dose according to the authorized product information. Clinical judgment should always be applied.
- Misuse of a medicinal product: situations where the medicinal product is intentionally and inappropriately used not in accordance with the authorized product information.
- Abuse of a medicinal product: persistent or sporadic, intentional excessive use of medicinal products which is accompanied by harmful physical or psychological effects.
- Drug exposure during pregnancy and/or breast-feeding.
- Lack of efficacy/effectiveness.
- Medication errors: are broadly defined as any error in the prescribing, dispensing, or administration of a drug, irrespective of whether such errors lead to adverse consequences or not.
- Occupational exposure: this refers to the exposure to a medicinal product, as a result of one's professional or non-professional occupation.
- Suspected Drug-drug interaction.
- (Suspicion of) Transmission of infectious agent.

Causality Assessment (relationship to efgartigimod):

The treating physician is obligated to assess the relationship between efgartigimod and each occurrence of each AE/SAE as related or not related. The treating physician will use clinical judgment to determine whether there is reasonable possibility that efgartigimod caused the AE. A reasonable possibility of a relationship conveys that there are facts, evidence, and/or arguments to suggest a causal relationship, rather than a relationship cannot be ruled out. Alternative causes, such as underlying disease(s), concomitant therapy, and other risk factors, as well as the temporal relationship of the event to efgartigimod administration, will be considered and investigated

Related means that the AE cannot be explained by the participant's medical condition, other therapies, or an accident. The temporal relationship between the AE and efgartigimod administration is compelling and/or follows a known or suspected response pattern concerning that efgartigimod.

Not related means that the AE can be readily explained by other factors such as the participant's underlying medical condition, concomitant therapy, or accident. No plausible temporal or biologic relationship exists between the efgartigimod and the AE.

There could be situations in which an AE/SAE has occurred and the treating physician has minimal information to include in the initial report. However, it is very important that the treating physician always assess causality for every event before the initial transmission of the AE/SAE data. The treating physician could change his/her opinion of causality in light of follow-up information and send an AE/SAE follow-up report with the updated causality assessment.

Severity

The severity of AEs and SAEs will be graded as mentioned below:

- **Grade 1:** Mild; asymptomatic or mild symptoms; clinical or diagnostic observations only; intervention not indicated
- **Grade 2:** Moderate; minimal, local or noninvasive intervention indicated; limiting age appropriate instrumental ADL (e.g., preparing meals, shopping for groceries or clothes, using the telephone)
- **Grade 3:** Severe or medically significant but not immediately life threatening; hospitalization or prolongation of hospitalization indicated; disabling; limiting self-care ADL (e.g., bathing, dressing and undressing, feeding self, using the toilet, taking medications, and not bedridden)
- **Grade 4:** Life-threatening consequences or urgent intervention indicated
- **Grade 5:** Death related to AE

NOTE: An AE that is assessed as severe may not necessarily meet the criteria for an SAE. Severe is a category used for rating the intensity of an event; and both AEs and SAEs can be assessed as severe. An event is defined as “serious” when it meets at least 1 of the predefined outcomes as described in the definition of an SAE, not when it is rated as severe. Grade 4 and 5 AEs are always assessed as serious (i.e., SAE).

Outcome assessment

One of five outcomes listed below must be recorded:

- **Recovered/Resolved** – The event has stopped. The stop date of the event must be recorded.
- **Recovering/Resolving** – The subject is clearly recovering from an event. The event is not yet completely resolved.
- **Not Recovered/Not Resolved** – The event is still ongoing. (Could include stable and commensurate with ongoing disease processes).
- **Recovered/Resolved with sequelae** – The event has reached a state where no further changes are expected, and the residual symptoms are assumed to persist. An example is hemiparesis after stroke.
The stop date of the event must be recorded. In case of an SAE, the sequelae should be specified.
- **Fatal** – The subject has died as a consequent of the event.
- **Unknown** – Unknown to investigator, e.g., subject lost to follow up.

Action taken:

- **Withdrawal** - the permanent discontinuation of efgartigimod when the participant stops receiving efgartigimod before the end of the study and does not resume receiving efgartigimod.

- **Interruption-** the temporary discontinuation of efgartigimod when the participant discontinues receiving efgartigimod before the end of the study and resumes once the cause for the discontinuation has been resolved

Pregnancy

If pregnancy is reported, the treating physician will record the pregnancy information on the appropriate form and submit it to the sponsor within 7 calendar days of learning of the pregnancy in the female participant or the female partner of the male participant. The participant and pregnant female partner, if consented, will be followed to determine the outcome of the pregnancy. The treating physician will collect follow-up information on the participant/pregnant female partner and the neonate and forward it to the sponsor. While pregnancy itself is not considered an AE or SAE, any pregnancy complication or elective termination of a pregnancy for medical reasons will be reported as an AE or SAE. Abnormal pregnancy outcomes (e.g., spontaneous abortion, fetal death, stillbirth, congenital anomalies, ectopic pregnancy) are considered SAEs and will be reported accordingly.

Contact details to report AEs/SAEs and Pregnancies to the sponsor:

•**Email:** [contact]

•**[contact]

